Facility Director for Main Site

[name]

Email: [contact]

Phone:

Study Details

Describe the purpose of the investigation. If this is a clinical trial, this should include a description of the disease and the goals of the research.

Chronic pain is a significant public health concern in the U.S., for which prescription opioids have historically been the standard treatment. This has resulted in striking rates of opioid use disorders and fatal overdoses. Identifying non-opioid medications for the management of chronic pain with minimal abuse liability is a public health necessity, and cannabinoids are a promising drug class for this purpose. More than 80% of medicinal cannabis users report pain as their primary medical indication. These patients tend to seek products that are low in delta-9-tetrahydrocannabinol (THC; the primary psychoactive, and thus intoxicating, component of cannabis), and high in cannabidiol (CBD), a cannabinoid that purportedly has therapeutic benefit for pain but does not produce intoxicating effects [1]. However, there are few well-controlled human laboratory studies assessing the efficacy of high-CBD cannabis for pain in the context of abuse, and even less is known regarding the effects of daily repeated use of cannabis on pain and its relationship to abuse liability. Carefully controlled research is needed. The proposed randomized, within-subjects, placebo-controlled 16-day crossover inpatient human laboratory pilot study (N = 16 healthy cannabis users; 8 men, 8 women) will address three important gaps in our understanding of the potential therapeutic utility of cannabis for pain: 1) If abruptly switching active cannabis (4.91% CBD/2.98% THC) to inactive cannabis (0% CBD/THC) increases experimental pain sensitivity, i.e. hyperalgesia, relative to baseline and if these effects parallel measures of cannabis withdrawal such as disrupted mood and sleep (Each cigarette contains approximately 39.28mg of CBD and 23.84mg of THC. They smoke 75% of one cigarette, so each dose is approximately 29.46mg of CBD and 17.88mg of THC); 2) If tolerance to the analgesic and abuse-related effects of cannabis is reversed following 7 days of abstinence from active-THC cannabis (by administering 0% CBD/THC, inactive cannabis); 3) If tolerance is present/develops to repeated, daily smoked cannabis (4.91% CBD/2.98% THC) administration on measures of experimental pain and abuse liability. Two distinct modalities of experimental pain will be assessed: The Cold Pressor Test (CPT) and Quantitative Sensory Testing Thermal Temporal Summation (QST-TTS). The study will start with a day of active cannabis administration (4.91% CBD/2.98% THC) given 3x/day in order to standardize cannabis exposure across participants (Day 1), and will be followed by a 7-day "inactive phase" (Day 2-8) in which participants will smoke inactive cannabis (0% CBD/THC) 3x/day during this 7-day period. The last 7 days (Day 9-15) will comprise an "active cannabis phase" in which participants will smoke cannabis (4.91% CBD/2.98% THC) 3x/day. Throughout the study, experimental pain and abuse-related effects will be assessed, as will sleep and subjective mood assessments. With rates of chronic pain increasing and limited availability of safe and effective treatment alternatives to opioids, this study will provide essential data regarding the efficacy of daily cannabis use on measures of analgesia and abuse liability and the consequences of cannabis abstinence on measures of pain, as it is possible that abrupt cessation of cannabis use will lead to worsened baseline pain.

General Overview:

This within-subjects study will examine the effects of daily repeated use of cannabis on pain and its relationship to abuse liability. Healthy, non-treatment seeking cannabis smokers (N=16, 8M, 8F) will be admitted to the research center on 5- South of NYSPI for a 16-day inpatient stay. On the first full inpatient day, participants will smoke active cannabis (4.91% CBD/2.98% THC). Days 2-8 will comprise the Inactive Phase, in which placebo cannabis (0% CBD/THC) will be administered 3x/day. The next 7 days (Day 9-15) will be the Active Phase, in which active cannabis (4.91% CBD/2.98% THC) will be administered at the same time points (Table 1). Participants will complete subjective effects visual analog scales and a cannabis rating form daily, and will complete the Cold-Pressor Test and Quantitative Sensory Testing-Thermal Temporal Summation on Days 1, 2, 5, 8, 9, 12, and 15 to explore three critical questions regarding cannabis' therapeutic utility for pain (as illustrated in Figure 1): 1) If abruptly switching active cannabis to inactive cannabis increases experimental pain sensitivity, i.e. hyperalgesia (Day 2-8; red bars) relative to baseline and if these effects parallel measures of cannabis withdrawal such as disrupted mood and sleep; 2) If pharmacological tolerance to the analgesic and abuse-related effects of cannabis is reversed following 7 days of abstinence from active-THC cannabis (by administering 0% CBD/THC, inactive cannabis): defined as a) a significant decrease in CPT latencies and QST-TTS response following active cannabis administration on Day 12 or Day 15 compared to Day 9 (Active Phase), and b) a significant decrease in subjective visual analog scale ratings of abuse, i.e. 'Good Drug Effect' following active cannabis administration on Day 12 or Day 15 (Active Phase) compared to Day 9 (Active Phase); 3) If tolerance is present/develops to repeated, daily smoked cannabis (4.91% CBD/2.98% THC) administration on measures of experimental pain and abuse liability (green bar): defined as a significant increase in CPT latencies and QST-TTS response and 'good drug effect' after active cannabis administration when Day 9 of the Active Phase is compared to Day 1.

Provide the hypothesis for this research.

Aim 1. Determine the effects of abstinence from active cannabis (by use of 0% THC cannabis) on experimental pain. We hypothesize that (a) abrupt abstinence will result in increased CPT and QST-TTS responses, indicative of withdrawal-induced hyperalgesia.

Aim 2. Determine if a) tolerance is present (Day 1) and is reversed following abstinence from active cannabis (Days 2-8); b) tolerance develops to daily smoked active cannabis (4.91% CBD/2.98% THC; Days 9-15) administration on pain and abuse liability measures. We hypothesize that: (a) existing analgesic tolerance will be reversed following abstinence from active cannabis; (b) over the course of the active cannabis phase, tolerance will develop to cannabis' analgesic but not abuse-related effects.

Include pertinent information about the relationship of the proposed research to previous studies and describe the significance of the proposed research. Be brief.

In an attempt to mitigate the ongoing opioid crisis, the CDC and NIH have urged the identification of non-opioid medications for chronic pain. Developing novel pain management approaches with lower abuse liability than opioids is a public health necessity. In light of the widespread legalization of cannabinoids (cannabis or components of the cannabis plant) across the U.S., use of these products is increasing both recreationally and medicinally. Many medicinal cannabis users indicate that they use cannabinoid products to assist with chronic pain management; of the >1.2 million registered medical cannabis patients across the U.S., the majority (>80%) cite pain relief as the primary reason for use. These legislative changes and use patterns are emerging in the absence of sufficient controlled scientific evidence supporting efficacy for pain. Specifically, most people using cannabinoids for pain do so on a daily and long-term basis, yet it is unknown how cannabinoid effects change with repeated use. Of the 100+ cannabinoids identified, the two major and most prominently used are delta9- tetrahydrocannabinol (THC) and cannabidiol (CBD). THC is the primary psychoactive component of cannabis and has been shown to exert analgesic effects by our laboratory (Cooper, 2013, p.1984), but its therapeutic utility occurs at concentrations associated with abuse liability. CBD, on the other hand, is non-intoxicating thus is not considered to have abuse liability. For this reason, products that are high in CBD content are being used at increasing rates for various medical conditions ranging from childhood seizures (for which it is FDA- approved as Epidiolex) to chronic pain.

A number of studies have shown combinations of CBD:THC to have analgesic efficacy and minimal abuse liability in populations with chronic pain, including HIV-related neuropathic pain and cancer pain. However, there is very little scientific evidence outside of medically-ill populations to support the therapeutic utility of CBD:THC combinations for pain relief in the context of abuse liability, particularly when used repeatedly. Further, while some studies suggest that CBD attenuates the adverse effects of THC (Osborne, 2017, p.310-324) other studies have demonstrated the opposite (Solowij, 2019, p. 17-35) or no effect at all ([name], 2016, p. 1974-1982). Despite mixed evidence for efficacy and abuse potential, people using cannabis medicinally often seek out products from dispensaries that are high in CBD and low in THC content due to the widespread belief that these products offer therapeutic benefit without abuse liability (Mead, 2017, p.288-291).

The consequences of daily use of combined smoked CBD:THC cannabis on pain outcomes or abuse-related effects are not known. An additional unknown is how cessation of daily use affects measures of pain. Cannabinoids can increase pain sensitivity at certain doses, but no studies have investigated if pain sensitivity increases as a function of abrupt cannabis abstinence. It is possible that cannabis' analgesic effects diminish with repeated use, resulting in increased use to overcome pharmacological tolerance. Further, abrupt cannabis cessation may result in hyperalgesia along with other symptoms of cannabis withdrawal, which would make maintaining abstinence difficult. These factors could worsen ongoing pain and increase the likelihood of developing cannabis use disorder. Finally, it is unknown if analgesic tolerance can be reversed following a period of abstinence from active cannabis. Currently, there are no data on these effects to inform patients using cannabis on a regular basis for pain.

Study Procedures

Research Procedures (Select all that apply):

- Data Analysis/ Chart Review
- Drug Study
- Device Study
- MRI w/ Contrast: MRIs for research purposes are subject to CBIN policy on Incidental Findings
- MRI w/out Contrast: MRIs for research purposes are subject to CBIN policy on Incidental Findings
- Interview/Survey/Questionnaire
- Blood Collection
- Sample Collection other than blood
- Non Invasive Physical Measurements
- Student Research
- Ionizing Radiation
- IV Infusion
- Genetic Research
- Transcranial Magnetic Stimulation (TMS)
- Transcranial Direct-Current Stimulation (tDCS)
- Requesting that NKI serve as the IRB for an institution outside of OMH/RFMH
- Establishment of a Research Repository

Sample Collection Other Than Blood

- Urine
- Cerebral Spinal Fluid (CSF)
- Other

Specify Other

COVID-19 nasopharyngeal swabs

Detail all questionnaires and assessments (including validated assessments) that will be used for this study.

These items can be explained or listed and attached. If the assessment or questionnaire is validated, please confirm that there have been no modifications to the document. If the study instrument is not a validated tool please attach the document with this submission.

Some assessments are conducted under a screening protocol (#7091R), while others are conducted under the study protocol (#8016), which is indicated below.

Screening Assessments (these assessments (which are validated and not modified from their original form) are conducted under screening protocol 7091R and are thus not part of protocol 8016, but are detailed for clarity in our procedures):

- 1) Telephone Interview: 15 min.
- 2) Timeline Follow-Back Interview for substance use: 10 min.
- 3) Drug Use History Questionnaire: 10 min.
- 4) General Health Questionnaire: 5 min.
- 5) Medical History Questionnaire: 10 min.
- 6) Beck Depression Inventory: 5 min.
- 7) General Pain Index Questionnaire: 5 min.
- 8) Structured Clinical Interview for DSM-5: 30 min.
- 9) 12-lead electrocardiogram: 15 min.
- 10) Laboratory Tests (blood count with differential chemistry profile, liver enzymes, and GGTP): 30 min.
- 11) Urinalysis with 12-panel urine drug testing: 5 min.
- 12) Physical and Psychiatric Examination: 30 min, unless there is an indication for a diagnosis, in which case it will be 90 min.

Experimental Assessments (conducted under protocol 8016):

- 1) The Cold Pressor Test (CPT) is a validated and reliable pain-induction procedure that reflects A-delta nerve fiber activity within the autonomic nervous system and closely mimics clinical chronic pain. CPT has been shown to have excellent reliability and predictive validity for medication-induced analgesia, including cannabinoids. For this task, two temperature- controlled circulating water baths maintain warm (36.5-37.5°C) and cold (3.5-4.5°C) water. Participants immerse their hand into a warm bath for 3 min (to standardize baseline skin temperature), then the cold bath, indicating when they first experience pain and withdrawing when the pain gets uncomfortable. Study staff will record time (in seconds) until participants: 1) report discomfort (pain threshold), and 2) withdraw their hand from the cold water (pain tolerance): 15 min.
- 2) Quantitative Sensory Testing-Thermal Temporal Summation (QST-TTS) uses repetitive fixed frequency and intensity heat stimulation to induce central sensitization of C-fibers in the spinal cord and is regarded as an experimental correlate of the 'wind-up' phenomenon in the dorsal horn. As dorsal horn CB-1 activity has been linked to suppression of 'wind-up' and central sensitization (the mechanism purportedly underlying cannabis' efficacy for neuropathic pain), cannabis use may decrease QST-TTS response, mirroring analgesia on the CPT during active cannabis administration vs. placebo. For this task, a Medoc TSA-II NeuroSensory Analyzer with a 30 x 30 mm Peltier thermode applies tonic noxious heat stimulation to the thenar eminence of the palm: the baseline temperature is 32.0°C, increases at a rate of 1°C/s up to 46.5°C, and remains constant for 120 sec. Total duration: 3 min.
- 3) Cold Pressor Test Visual Analog Scale (CPT-VAS): 11-item questionnaire rating the physiological and subjective effects of the cold water on a 100 mm VAS after the CPT: 15 sec.
- 4) Quantitative Sensory Testing-Thermal Temporal Summation Computerized Visual Analog Scale (CoVAS): Participants rate magnitude of perceived pain on a 100 mm VAS during the QST-TTS: 135 sec.
- 5) Physiological response to pain: Heart rate and blood pressure will be measured throughout pain assessments: 2 min.
- 6) Pain Intensity/Bothersomeness Scale (PIBS): Ratings of CPT and QST pain on a 0-to-10 scale: 0 being 'not painful/bothersome at all' and 10 being 'most painful/bothersome feeling imaginable': 10 sec.
- 7) Subjective Effects: A series of 100 mm VAS in which participants indicate how they are feeling at that

moment will be completed 3x/day. The 44-item VAS includes mood, physical symptom, and drug effect descriptors. Based on a cluster analysis, we employed arithmetic means of individual item scores to reduce 34 of the 44 items into eight subscales: good drug effect; miserable; irritable; anxious; bad effect; social; and confused. We also analyze individual VAS drug craving ratings. These subjective measures may detect changes in abuse-related effects as well as changes in mood (miserable, irritable, anxious, cannabis craving) as a function of cannabis condition: 3 min.

8) Objective Sleep Measures: Participants will wear an Actiwatch Activity Monitoring System that tracks gross motor activity (Actiwatch®: Respiromics Company, Bend, OR) and records objective sleep outcomes (hours slept, number of awakenings). We have used this system effectively to demonstrate perturbations in sleep as a function of cannabis withdrawal.

9) Sleep Questionnaire: Participants will complete a sleep questionnaire which consists of a 7-item, 100 mm VAS instrument that assesses the quality of sleep and how many hours slept the previous night and wakefulness in the morning. Participants will be asked to rate symptoms by placing a mark on a line representing a continuum from "not at all" (on the left of the line) to "extremely" (on the right of the line) indicating how the phrase relates to the last night's sleep: 30 sec.

10) Cannabis Rating Form (CRF): Participants rate the strength, liking, desire to take again, good drug effect and bad drug effect of cannabis on a 100mm VAS: 2 min.

Please attach all Questionnaires and Assessments listed above.
No answer provided.

Describe the procedures in sufficient detail so that a reviewer, who is not familiar with them, can comprehend what is to be done and can evaluate any risks.

This study is now in data analysis only, and the following procedures describe the study as it was approved and conducted during the COVID era.

Consent Procedures:

Step 1 (conducted under #7091R). After initial determinations of eligibility (e.g. current drug use patterns, attitude about treatment) obtained via the telephone interview, volunteers will be emailed a secure link to a Qualtrics survey containing assessments regarding demographic and medical information, thereby eliminating the need for subjects to travel to NYSPI to complete these questionnaires and thus reducing their risk of exposure to COVID-19 by traveling to the institution or while on site. They will be asked to review our screening and evaluation consent form (IRB #7091R), as well as the study consent form, HIPAA form and NYSPI privacy practices. Copies of the study consent form and the HIPAA form will be sent to participants via encrypted email. Participants will be required to select YES/NO to indicate whether they reviewed these documents and agree to complete the assessments before they may continue.

Step 2 (conducted under #7091R). Interviews with a trained psychologist will occur via HIPAA-compliant virtual telemedicine platforms such as Apple Facetime or Webex, once again minimizing the risk of exposure to COVID-19 that would exist if requiring all subjects to travel to NYSPI for an in-person interview. Psychologists (Drs. [name], [name], [name], [name]) will conduct interviews regarding drug use and psychiatric symptoms and will provide a detailed explanation of the procedures outlined in the consent form. If the volunteers are eligible for continued screening after the PhD interview, they will be invited for a single in-person screening visit to review the study consent form, complete medical assessments, and be tested for COVID-19. A dated note-to-file will be included in the participant's chart of the remote/verbal consent procedure documenting the consent discussion and review of the consent form, along with the participant's electronic agreement of the consent, as signed by the consenter.

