Since we will recruit moderate-heavy cannabis users with varied use patterns, they will enter the study with varying pharmacological tolerance. Therefore, Study Day 1 will be an initial day of active cannabis administration to standardize exposure to the same strength of smoked cannabis across participants prior to enforced abstinence from active cannabis in the Inactive Phase (Day 2-8). Participants will be administered active cannabis (two one 4.91% CBD/2.98% THC cigarettes) at 1000h, 1300h, and 1600h.

Days 2-8 (Inactive Phase)

On Study Days 2-8, participants will be administered one inactive cannabis cigarette (0.00% CBD/THC) at the same three time-points (1000, 1300, 1600). We have shown that inactive cannabis controls for expectancy effects of smoking, producing small but reliable increases in ratings of 'high' [5]. Therefore, this phase will assess how abstinence from active- THC cannabis affects pain outcomes in parallel to measures of cannabis intoxication and withdrawal (mood, sleep).

Days 9-15 (Active Phase)

On Study Days 9-15 participants will be administered an active cannabis cigarette (one 4.91% CBD/2.98% THC cigarette) at the same three time-points (1000, 1300, 1600), with the exception of Day 15 where they will be administered active cannabis only at 1000. This phase will allow us to see if CPT and QST pain outcomes and abuse liability change over time

Move Out

Following completion of all assessments of Day 15, the PI will discuss with the participants benefits of cannabis cessation, highlighting availability of a range of treatment options, prior to discharge. At 180 minutes post-cannabis administration, participants will complete field sobriety tests, vital signs, and a Mini-Mental State Exam (MMSE), and will be permitted to leave once they meet discharge criteria. Criteria for discharge will be met when participants report no ongoing subjective drug effects and have no signs of impairment or intoxication, pass the field sobriety test, have normal vitals, and a normal mental status score as assessed by the MMSE. [name], [name], or [name] will make the final determination that the patient is sober and medically stable and can leave the facility.

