The effects of smoked cannabis are typically gone within 3 hours. In the rare event that a participant is still impaired at the conclusion of Study Day 15, they will be asked to remain in the laboratory until the effects wear off, and will be paid extra (i.e., \$10 per hour for any additional time they remain in the laboratory). Participants may be sent home in a taxi, for which they will be reimbursed. They will be allowed to leave the facility when they pass the field sobriety test and are medically stable. They will be instructed not to drive a car or use other drugs or alcohol for 8 hours after administration of cannabis; therefore, participants will be required to take public transportation (i.e., bus or subway) from the laboratory on Day 15, for which they will be reimbursed (included in their pay for Day 15).

CPT and QST-TTS

On Days 1, 2, 5, 8, 9, 12, and 15, participants will complete the CPT and QST-TTS pain tasks 30 minutes before the 1000h cannabis administration (baseline), and 0, 15, 30, 45, 60, and 90 minutes post-cannabis administration. Participants will also complete measures of CPT-induced discomfort (CPT-VAS, PIBS) and will continuously rate the magnitude of perceived pain for the temporal heat stimulation of the QST-TTS (Co-VAS) at these time-points. On these days of pain testing, except for Day 15, participants will also complete a cannabis rating form and subjective effects visual analog scales pre-cannabis administration (0945h), for a full-time course after the first cannabis administration (1015h, 1045h, 1115h, 1145h, 1215h), and after each subsequent cannabis administration timepoint (1315h, 1615h). On Day 15, these assessments will conclude with the 1215 time-point. Vital signs will be taken before and after each pain assessment. In addition, vital signs will be taken halfway through the duration of each CPT assessment. If vital sign parameters are exceeded at any point during the CPT task, staff will follow the same assessment procedures as stated in the training section above.

On days when there are no pain assessments, participants will complete just the cannabis rating form and subjective effects battery at 1015h, 1315h, and 1615h.

Cannabis Administration

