Title: Repeated Cannabis Administration on Experimental Pain and Abuse Liability

NCT: 04576507

Document date: April 14, 2025

Statistical Analysis

Overview: All data analyses will be based on models using repeated measures analysis of variance (RM-ANOVA) analyzed as a function of cannabis condition (active vs. inactive) and day (Day 1-15), and sets of planned comparisons, calculated with SPSS or SUPERANOVA statistical packages. The planned comparisons are *a priori*, and designed to test the specific hypothesis for each aim. Tests of differences for all comparisons will be based on F-statistics with degrees of freedom corrected, depending on the observed within-subject correlation of the measures, using the method of Geiser and Greenhouse or Huynh and Feldt. Results will be considered statistically significant at $p < 0.05$, using 2-tailed tests. Distribution of demographic variables (ethnicity, age, sex) will be described in terms of means, standard deviations, proportions, and 95% confidence intervals, where appropriate.

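### Aim 1's day labels misplace the Day 2 and Day 9 pre-dose pain tests, and its comparison with an undefined baseline is confounded with repeated testing

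*Protocol*

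**What the plan says.** Question 1 in the protocol's General Overview asks about "hyperalgesia (Day 2-8; red bars) relative to baseline". The Day 1 (Standardization) section likewise treats these days as "enforced abstinence from active cannabis in the Inactive Phase (Day 2-8").

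Active cannabis is given on Day 1 ("cigarettes) at 1000h, 1300h, and 1600h"). It resumes at 1000h on Day 9 on the same three-times-a-day schedule, "with the exception of Day 15 where they will be administered active cannabis only at 1000". Everyone follows this one order.

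The CPT and QST-TTS section sets pain testing on Days 1, 2, 5, 8, 9, 12 and 15. On each of these days "participants will complete the CPT and QST-TTS pain tasks 30 minutes before the 1000h cannabis administration (baseline"), which is 0930h, and tests are repeated after dosing.

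The SAP says that data will be "analyzed as a function of cannabis condition (active vs. inactive) and day (Day 1-15), and sets of planned comparisons". The protocol's Statistical/Data Analysis Plan says that the comparisons follow, but neither document lists any. Neither says which baseline question 1 means, whether Aim 1 uses pre-dose or post-dose readings, or how test repetition is handled. Days 12 and 15 are named for tolerance in question 2, not as a return-to-active comparator for question 1.

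**The concern.** A test at 0930h, before that day's first cigarette, reflects what was smoked up to the previous afternoon. A label based on what is smoked later that day does not describe the state being measured. Grouped by label, the first resting test after the standardised active day counts as abstinence, and the test after the longest abstinence counts as active. Either error pulls a real withdrawal hyperalgesia towards zero.

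Separately, every Day 2-8 test comes after Day 1. Sensitisation to repeated pain testing could mimic hyperalgesia in that comparison, and habituation could hide it. The design runs active, inactive, active, so pain after the return to active cannabis is the trial's own evidence for separating abstinence from drift. Question 1 does not call on it.

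**Working it through.** **The plan's own figure.** The sample-size justification assumes d = 0.7, within-subject correlation 0.6 and 4 dropouts from 24: 24 − 4 = 20 completers. For one paired difference, dz = 0.7/√(2 × (1 − 0.6)) = 0.783, which gives 91.3% power at n = 20 (two-sided 5%). So 20 is consistent with its inputs, though no power target is stated. The General Overview says N = 16, where power is 83.3%.

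**Step 1: hours since the last active cigarette at the 0930h test.** The gap is 24 × (test day − last active day) + 9.5 − 16.

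| Test day | Last active | Hours | Label |
|---|---|---|---|
| 2 | Day 1, 1600h | 17.5 | inactive |
| 5 | Day 1, 1600h | 89.5 | inactive |
| 8 | Day 1, 1600h | 161.5 | inactive |
| 9 | Day 1, 1600h | 185.5 | active |
| 12 | Day 11, 1600h | 17.5 | active |
| 15 | Day 14, 1600h | 17.5 | active |

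The Day 1 pre-dose test precedes standardisation and reflects the participant's own earlier use.

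**Step 2: contrasts on the pre-dose readings.** Number the test days 1 to 7 as sessions. Assume the full effect on Days 5, 8 and 9, none on Days 1, 2, 12 and 15, and drift linear in session.

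- *Reading A*, mean(2, 5, 8) − Day 1. Effect kept: (0 + 1 + 1)/3 = 0.667. Drift: (2 + 3 + 4)/3 − 1 = +2 sessions. Sum of squared weights: 1/3 + 1 = 1.333.
- *Reading B*, by label, mean(2, 5, 8) − mean(1, 9, 12, 15). Effect kept: 2/3 − 1/4 = 0.417. Drift: 3 − (1 + 5 + 6 + 7)/4 = −1.75 sessions. Sum of squares: 1/3 + 1/4 = 0.583.
- *Onset leg*, mean(5, 8, 9) − Day 2. Effect kept: 1. Drift: 4 − 2 = +2.
- *Reversal leg*, mean(5, 8, 9) − mean(12, 15). Effect kept: 1. Drift: 4 − 6.5 = −2.5.
- *Combined*, mean(5, 8, 9) − [w × Day 2 + (1 − w) × mean(12, 15)]. Zero drift needs 2w + 6.5(1 − w) = 4, so w = 2.5/4.5 = 0.556. Effect kept: 1. Sum of squares: 1/3 + 0.556² + 0.444²/2 = 0.741.

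The two legs carry drift of opposite sign, so drift in one direction cannot by itself make both agree. Readings A and B also carry drift of opposite sign, so the unstated choice between them matters.

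**Step 3: size on the planning values.** The contrast SD is √(0.4 × sum of squares). For Reading A it is √(0.4 × 1.333) = 0.730; the effect is 0.667 × 0.7 = 0.467 SD; dz = 0.639; power is 77% at n = 20 and 67% at n = 16. For Reading B, power at n = 20 is 73%.

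The documents give no drift size. At an assumed 0.1 SD per session, Reading A is biased by 2 × 0.1 = 0.2 SD. With no true effect it then rejects 21% of the time at n = 20; at 0.2 SD per session, 64%. Reading B rejects 34% and 87%. The combined contrast stays at 5%.

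**Step 4: sensitivity.** Suppose a fraction f of the effect is already present at 17.5 h and Day 1 carries none. Reading A keeps (f + 2)/3 and the combined contrast keeps 1 − f. The ratio of effect to standard error, combined to A, is [(1 − f)/√0.741] ÷ [((f + 2)/3)/√1.333]. It is 2.0 at f = 0, 1.34 at f = 0.25 and 0.80 at f = 0.50.

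Non-linear drift does not cancel fully. If drift follows the logarithm of session number, the combined contrast retains 0.149 units, against 1.059 for Reading A.

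**The case against.** The strongest reply is that Reading A is not in the documents. Baseline is undefined, the comparisons are unlisted, and Figure 1, to which the red bars belong, is not available here. A reader might infer that the trial has committed to mean(2, 5, 8) minus Day 1. It has not, and the 67% and 42% are conditional on a reading. The misplacement of Days 2 and 9, however, follows from the clock times wherever pre-dose readings are grouped by day label.

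A reader might also infer that the return to active cannabis is left out of the analysis altogether. That goes too far: Days 9, 12 and 15 enter the repeated-measures ANOVA. What is missing is their use as a reversal comparison for question 1, with Day 9 pre-dose on the abstinent side.

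Day labels are accurate for post-dose readings. But post-dose readings on active days measure acute cannabis effect, so an active-inactive difference there mixes lost analgesia with hyperalgesia. If baseline means the same day's pre-dose test, the abstinence state is subtracted out.

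Three further points stand as limits. Equal hours do not mean equal states: Day 2 follows one standardised day on top of varied prior use, while Days 12 and 15 follow three and six active days after a week without, and Aim 2 itself expects tolerance to change over that span. A training session before admission may absorb some early habituation. And it is tempting to say that regrouping doubles efficiency whatever the onset time. Step 4 shows otherwise: 2.0 persists under early onset only if Day 1 pre-dose carries the same fraction, which the documents cannot establish.

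**Conclusion.** The concern holds in this form: for pre-dose readings, the day labels put Day 2 and Day 9 on the wrong side by time since active cannabis; the Aim 1 comparison is not defined; and a comparison of Days 2-8 with Day 1 cannot separate abstinence from repeated testing.

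The loss is about a third of the effect under Reading A and more than half (7/12) under Reading B, if nothing is present at 17.5 h. If half the effect were present then and none on Day 1, Reading A would keep 83%. The drift bias is two sessions' worth under Reading A, of unknown size and sign. The documents do not show that drift occurs, or that Day 2 is free of withdrawal. They show only that the comparison could not tell. The remedy uses readings already scheduled, so the point is worth acting on, but it does not invalidate the trial.

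**What to change.** In the SAP, define Aim 1 on the pre-dose CPT and QST-TTS readings:

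- Abstinent days are 5, 8 and 9. Do not count Day 2 pre-dose as established abstinence.
- Report the onset leg (Days 5, 8, 9 against Day 2), with Day 1 pre-dose also shown, and the reversal leg (Days 5, 8, 9 against Days 12 and 15). Attribute a change to withdrawal rather than test repetition only if both legs point the same way.
- Add as a supporting analysis the combined contrast with weights 0.56 on Day 2 and 0.44 on the mean of Days 12 and 15. These weights are one reasonable choice, not the only one.
- State the assumption that Days 12 and 15 have returned to the non-abstinent state; a single fixed sequence cannot test it.

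No new data are needed, but this is more than an edit of wording. The protocol says that the study has reached the analysis stage, and it describes blinding of the participant only. If outcome data have been examined, the analysis must be labelled post hoc. Participants who leave before Day 12 contribute only the onset leg. The contrast is conservative if hyperalgesia is already present at 17.5 h or if reversal is incomplete.
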